1.0 INTRODUCTION

This document is the Clinical Investigation Plan (CIP) for the Regent China Post-Market Clinical Follow-up (RC-PMCF) Study. RC-PMCF is a prospective, multi-center observational study of the safety and performance of the Regent™ Mechanical Heart Valve (Regent MHV) used as a replacement valve in patients with a diseased, damaged, or malfunctioning aortic valve. This clinical study is sponsored by Abbott.

The purpose of the RC-PMCF study is to meet the post-market clinical follow-up (PMCF) requirements of the National Medical Products Administration (NMPA). The primary objective of this clinical study is to confirm the safety and performance of Abbott's Regent MHV for the replacement of native or prosthetic aortic valves in a Chinese population. The RC-PMCF study will prospectively follow 200 subjects implanted with a Regent MHV during surgical replacement of the aortic valve at up to 10 clinical centers through 5 years post-implant.

This clinical investigation will be conducted in accordance with this CIP. All investigators involved in the conduct of the clinical investigation will be qualified by education, training, or experience to perform their tasks, and this training will be documented appropriately.

1.1 **Background and Rationale**

1.1.1 **Background**

Surgical intervention is one of the most effective therapies currently available for valvular heart disease (VHD) and has a significant survival benefit with relatively low perioperative mortality and morbidity. It is estimated that there are over 300,000 heart valve replacement surgeries performed worldwide each year¹, and this number is expected to triple by 2050.² Mechanical heart valve replacement is one of the options for surgical intervention and has been used for over 40 years to successfully treat VHD. Abbott's MHVs have been implanted in nearly 3 million patients and are estimated to account for 34% of implants in patients under the age of 30 undergoing aortic valve surgery.²

Historically, the clinical experience of more than 40 years with the Abbott MHVs has been favorable.³⁻⁷ Clinical outcomes have demonstrated that the bileaflet design is more durable than bioprosthetic valves^{1,8} and can last over 30 years.¹

The Regent MHV is indicated for patients requiring the replacement of a diseased, damaged, or malfunctioning native aortic heart valve. It may also be used as replacement for previously implanted aortic prosthetic heart valves. Patients with failing aortic valves require intervention to avoid heart failure and related adverse events (AEs) such as mortality. Recommendations from clinical practice guidelines and consensus statements published by global heart and cardiology societies suggest surgical interventions, including valve replacement, in symptomatic patients with aortic stenosis⁹⁻¹¹ or aortic regurgitation.^{9,10} Without intervention, patients with a malfunctioning aortic valve have a poor long-term prognosis.

The safety and performance of the Regent MHV have been previously established,^{3,5,12-24} and the clinical evidence demonstrates continued safety and performance of the Regent MHV when used under the conditions and for the purposes intended. However, the Regent MHV has not been evaluated in a

Clinical Investigation Plan

prospective study in the Chinese population. The purpose of the RC-PMCF study will confirm the safety and performance of the Regent MHV in a Chinese patient population.

1.1.2 Rationale for Conducting this Clinical Investigation

The objective of this study is to confirm the continued safety and performance of the Regent MHV to meet the PMCF requirements of the NMPA.

Device safety will be evaluated by comparing freedom from valve-related mortality in subjects implanted with a Regent MHV during aortic valve replacement to predefined clinical acceptance criteria based on the surgical literature. Regent MHV device performance will be evaluated based on durability by comparison of valve-related reintervention in the replaced valve to predefined clinical acceptance criteria based on the surgical literature.

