4.1 Primary Endpoints and Rationale

The primary safety endpoint is freedom from valve-related mortality at 5 years. Reasons for selection of this primary safety endpoint include its correlation with severe device- and procedure-related adverse events and the frequent reporting of this outcome in the published literature on surgical MHVs. [REDACTED]

The primary performance endpoint is freedom from valve-related reoperation at 5 years. Reasons for selection of reoperation on the MHV is an indicator of both the performance and durability of the original MHV implant procedure and is often reported in the published literature on MHVs. [REDACTED]

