4.2 Descriptive Endpoints

This section lists descriptive endpoints that will be summarized using descriptive statistics and compared to the objective performance criteria as defined in ISO5840-2:2021 for mechanical heart valves or acceptance criteria if appropriate.

- Annualized rate from the following events from implant through five years post-implant:
 - All-cause mortality
 - Reintervention
 - Major bleeding
 - Thromboembolism
 - Valve thrombosis
 - Endocarditis (Operated Valve)
 - Major Paravalvular Leak
- NYHA (New York Heart Association) Functional Class at baseline and annually post-implant

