8.2.2 Primary Performance Endpoint Analysis

The primary performance endpoint is freedom from valve-related reoperation. [REDACTED]

Freedom from reintervention on the replaced valve is an indicator of both the performance and durability of the original replacement procedure and is often reported in the surgical literature on valve replacement. [REDACTED]

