8.2.3 Descriptive Endpoints

The following descriptive endpoints will be summarized as % events per valve-year. Major bleeding, thromboembolism, valve thrombosis, endocarditis and major paravalvular leak will be assessed at 5 years, and descriptively compared to 2 times the objective performance criteria as defined in ISO5840-2:2021 for mechanical heart valves. All-cause mortality and reintervention will be assessed at 5 years, and descriptively compared to acceptance criterion, as outlined below:

- Annualized rate of all-cause mortality (Acceptance criterion = [REDACTED])
- Annualized rate of reintervention (Acceptance criterion = [REDACTED])
- Annualized rate of major bleeding (OPC = 1.6% per valve-year)
- Annualized rate of thromboembolism (OPC = 1.6% per valve-year)
- Annualized rate of valve thrombosis (OPC = 0.1% per valve-year)
- Annualized rate of endocarditis (OPC = 0.3% per valve-year)
- Annualized rate of major paravalvular leak (PVL) (OPC = 0.3% per valve-year)

Valve dysfunction will be assessed by echocardiogram at 6 months and annual visits.

NYHA Classification will be assessed at baseline and annual visits.

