8.6 Multiplicity

No formal hypothesis testing will be performed in this study; therefore, adjustments for multiplicity will not be made.

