8.8 Planned Interim Analysis

No interim analyses are planned for this study. An annual study report will be generated during each calendar year. All enrollment and follow-up data collected since the study inception up till a pre-determined cut-off date will be prepared in the annual study report and submitted to NMPA to support the renewal of Regent registration. A final report will be prepared following study completion.

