### 3.5 Descriptive Endpoints or Additional Data

The following descriptive endpoints will be summarized as % events per valve-year. Major bleeding, thromboembolism, valve thrombosis, endocarditis and major paravalvular leak will be assessed at 5 years, and descriptively compared to 2 times the objective performance criteria as defined in ISO5840-2:2021 for mechanical heart valves. All-cause mortality and reintervention will be assessed at 5 years, and descriptively compared to acceptance criterion, as outlined below:

- Annualized rate of all-cause mortality (Acceptance criterion = 5% per valve-year)
- Annualized rate of reintervention (Acceptance criterion = 5% per valve-year)
- Annualized rate of major bleeding (OPC = 1.6% per valve-year)
- Annualized rate of thromboembolism (OPC = 1.6% per valve-year)
- Annualized rate of valve thrombosis (OPC = 0.1% per valve-year)
- Annualized rate of endocarditis (OPC = 0.3% per valve-year)
- Annualized rate of major paravalvular leak (PVL) (OPC = 0.3% per valve-year)

NYHA Classification will be assessed at baseline and annual visits.

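### Does Protocol 1.1.2 shift the performance judgement from reoperation to the looser, descriptive reintervention rate?

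*Protocol*

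**What the plan says.** Protocol 1.1.2 explains in two sentences how the study will judge the valve. Safety is judged on valve-related mortality. For performance, "Regent MHV device performance will be evaluated based on durability by comparison of valve-related reintervention in the replaced valve to predefined clinical acceptance criteria", and the sentence goes on to say that these criteria come from the surgical literature.

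The endpoint section uses a different word: "The primary performance endpoint is freedom from valve-related reoperation at 5 years". Reoperation is also the term in the opening sentence of Protocol 8.2.2, in the summary in Appendix X, and in SAP 1.4.2 and 2.3.1. Later in Protocol 8.2.2 the rationale returns to the other term: "Freedom from reintervention on the replaced valve is an indicator of both the performance and durability of the original replacement procedure".

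Reintervention is also an endpoint in its own right. Protocol 4.2 and SAP 1.4.3 list it under "Annualized rate from the following events from implant through five years post-implant". Protocol 8.2.3 says "All-cause mortality and reintervention will be assessed at 5 years, and descriptively compared to acceptance criterion, as outlined below"; the number is redacted there but visible in SAP 3.5: "Annualized rate of reintervention (Acceptance criterion = 5% per valve-year". Appendix II defines reintervention to cover catheter-based and enzymatic procedures as well as surgical reoperation. The visible part of Appendix II has no entry for reoperation.

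**The concern.** The two words are not synonyms in this protocol, and each belongs to a different endpoint. Section 1.1.2 is where the reader learns how performance will be judged, and it uses the word that belongs to the descriptive endpoint. The only criterion for that endpoint visible in either document is 5% per valve-year, which is generous beside the plan's other limits.

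Comparison with a criterion also carries the whole conclusion, since "No formal hypothesis testing will be performed in this study; therefore, adjustments for multiplicity will not be made". Annual reports are "submitted to NMPA to support the renewal of Regent registration", and they will be written before five-year reoperation results are complete. If 1.1.2 were followed to the letter, a report could call performance confirmed because the annualized reintervention rate was under 5%, while the primary endpoint missed its own criterion.

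**Working it through.** **1. The size of the 5% criterion.** Inputs: 200 implanted subjects (Protocol 8.3, SAP 2.4), five years of follow-up (Protocol 3.0), 5% per valve-year (SAP 3.5). The documents show no derivation of the 5%, so there is no planned figure to reproduce.

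- Maximum exposure: 200 × 5 = 1,000 valve-years. Events at the limit: 0.05 × 1,000 = 50.
- Five-year freedom under a constant hazard: exp(-0.05 × 5) = 0.779. With annual compounding: 0.95^5 = 0.774. Subjects with an event: 200 × (1 - 0.779) ≈ 44.
- Twice the objective performance criteria for valve thrombosis, endocarditis and major paravalvular leak: 0.2 + 0.6 + 0.6 = 1.4% per valve-year, and 5 / 1.4 = 3.6. Other causes of reintervention are outside this sum.
- Poisson chance of more than 50 events in 1,000 valve-years, for assumed true rates of 3% and 4%: 0.0003 and 0.053.

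So 5% is hard to exceed. That matters only if 1.1.2 refers to it.

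**2. Which endpoint 1.1.2 refers to.** Its features compare as follows.

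| Feature | Protocol 1.1.2 | Primary performance endpoint | Descriptive reintervention |
|---|---|---|---|
| Qualifier | valve-related | valve-related | none |
| Named alongside | valve-related mortality | valve-related mortality | all-cause mortality |
| Source of criterion | surgical literature | systematic literature review (Protocol 3.2, Appendix III) | not visible |
| Word used | reintervention | reoperation (reintervention in the 8.2.2 rationale) | reintervention |

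Every feature except the word itself points to the primary endpoint. Sections 4.1 and 8.2.2 supply further evidence: they give nearly the same justification for the primary performance endpoint, the first using reoperation and the second reintervention. The authors treat the words as interchangeable in rationale text, and 1.1.2 is rationale text.

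**3. Direction.** Reintervention contains reoperation. In the same subjects with complete follow-up, freedom from valve-related reintervention cannot exceed freedom from valve-related reoperation. Against one and the same criterion, the word in 1.1.2 therefore gives the stricter test. It is looser only if the 5% is brought in as well, and step 2 gives no ground for that.

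**4. Effect on the count.** Suppose a subject has only a catheter-based or enzymatic procedure on the valve. Whether that case counts moves the five-year estimate by about 1/200 = 0.5 percentage points: one case 0.5, two cases 1.0, four cases 2.0. The documents give no expected number of such cases. Protocol 7.3.1 requires every reintervention on the replaced valve to be reported, and Appendix II asks for open surgical and percutaneous procedures to be listed separately, so both counts will be available.

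**The case for a change.** The strongest reply is that a primary endpoint should not depend on which section is read. The mixed wording occurs twice, once inside the primary analysis section, and the visible definitions do not say whether a catheter procedure is a primary event. With no test planned and regulatory reports due each year, ambiguous wording could be used selectively. SAP 2.5 does allow interim descriptive reports for regulatory purposes. If the hidden primary criterion were 90% or 95% freedom (assumed values), and nearly all reinterventions were reoperations, results from 77.9% up to that value would meet the 5% limit and miss the primary one, a window of 12.1 or 17.1 points.

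The inconsistency itself stands: the two words differ by the protocol's own definition. The missing visible definition also stands as an observation, though one may sit in redacted text. The windows do not stand as evidence about this plan, because they depend on criteria nobody outside the sponsor can see. The reporting scenario is weak as well. Reintervention is to be assessed at five years, Protocol 8.4 and SAP 2.6 place the analyses after five-year follow-up or withdrawal, and Protocol 8.8 speaks of enrolment and follow-up data in the annual reports, with no comparison against 5%. Both documents already call that comparison descriptive, so a further disclaimer would add little.

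**Conclusion.** The concern does not hold. Section 1.1.2 describes the primary performance endpoint under a loose name and does not replace it with the descriptive 5% comparison. The conversion of 5% per valve-year to about 78% freedom is correct but has no bearing on how performance is judged.

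What is left is a clerical inconsistency in two rationale sentences. An analyst will work from the endpoint statements in Protocol 4.1 and SAP 1.4.2 and 2.3.1, which agree. The one open point of interpretation is whether a catheter-only or enzymatic procedure counts, at about 0.5 points per case. The ordinary surgical sense of reoperation, which Appendix II itself sets apart from catheter-based procedures, settles it sensibly, and the separate listing lets any reader check the alternative.

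This rests on two assumptions: that the redacted primary criterion was derived for the endpoint named in Protocol 4.1, and that redacted text does not redefine that endpoint. Nothing visible in either document suggests otherwise. Harmonising the word would be tidy but would alter no planned estimate.

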2.0 CLINICAL INVESTIGATION OVERVIEW

2.1 Clinical Investigation Objective

The objective of this clinical investigation is:

- To confirm the long-term safety and performance of Abbott Medical's Regent, model AGN-751 and AGFN-756, for replacement of native or prosthetic aortic valves in a Chinese population.

2.2 Device Used in the Clinical Investigation

2.2.1 Name of the Device Used

Regent MHV models to be used in this study are listed in Table 1. Each device is available in multiple sizes to allow treatment of native or prosthetic valve annuli with varying dimensions.

Table 1. List of Devices Used

Device name	Model Number/Sizes	Manufacturer	Market released
Regent™ – Standard cuff	AGN-751 Sizes 17-29mm	Abbott (formerly SJM) [name]	United States (2002) European Union (1999) China (2007) Canada (2000) Australia (2001) Japan (2004) Brazil (2008)
Regent™ – FlexCuff™	AGFN-756 Sizes 17-29mm		

2.2.2 Indication for Use

[figure not shown]
[figure not shown]
The Regent MHV is indicated for use as a replacement valve in patients with a diseased, damaged, or malfunctioning aortic valve. This device may also be used to replace a previously implanted aortic prosthetic heart valve.

Clinical Investigation Plan

2.2.3 Description of the Device(s) Under Investigation

[figure not shown]
The Regent MHV is a low-profile, center-opening device composed of a pyrolytic carbon orifice and two pyrolytic carbon elliptically shaped carbon leaflets. A sewing cuff fabricated of knitted polyester fabric is attached to the orifice. Figure 1 represents the general construction of the leaflet and orifice pivot design of the Regent MHV.

Figure 1. General Construction of the Regent MHV

Clinical Investigation Plan

Figure 2. Leaflet Positioning Within Orifice

The cuff material allows for rapid, controlled endothelial ingrowth over the sewing cuff surface. The sewing cuff is attached to the carbon orifice by a radiopaque metal band and is available in Standard Cuff and FlexCuff™ configurations. The FlexCuff™ provides an extended flange area for suture placement. Three suture markers are located on the valve sewing cuff to provide reference points for valve orientation and suture placement.

Additional information regarding the Regent MHV is available in the Instructions for Use (IFU).

3.0 CLINICAL INVESTIGATION DESIGN

The RC-PMCF is designed to meet the PMCF requirements of the NMPA. This is a prospective, observational, multi-center study of subjects clinically indicated for implantation of a Regent MHV. Two hundred subjects that enroll and undergo surgical aortic valve replacement using a commercially available Regent MHV will participate.

Study enrollment will occur at up to 10 centers in China. The study will enroll subjects expected to be implanted with a Regent MHV who meet all study eligibility requirements. Subjects who do not undergo the Regent MHV implant within 60 days of enrollment will be withdrawn from the study and will not contribute to the study sample size.

Subjects will be followed for 5 years post-implant; [REDACTED]

[figure not shown]
[REDACTED]. Study visits or data collection will occur at baseline, implant, discharge, 3 months, 6 months, and annually through 5 years post-implant.

3.1 Clinical Investigation Procedures and Follow-up Schedule

The process of subject screening and enrollment and the timing of data collection by study visits are summarized in **Figure 3**. Scheduled data collection will occur at a pre-implant baseline visit, implant, discharge, 3 months, 6 months, and then annually through 5 years post-implant.

Clinical Investigation Plan

Figure 3: Clinical Investigation Flow Chart

Clinical Investigation Plan

3.2 Measures Taken to Avoid and Minimize Bias

The study will include the following measures to minimize bias in the conduct of the study and analysis of clinical data:

- Inclusion and exclusion criteria are broad to reflect the population being treated and comparable to the literature
- Consideration of subjects assessed for aortic valve replacement at each site for inclusion in the study
- Expected values for the primary safety and performance endpoints have been predefined from a systematic literature review (Section **Error! Reference source not found.**).
- Maintaining high rates of follow-up compliance

3.3 Suspension or Early Termination of the Clinical Investigation

While no formal statistical rule for early termination of the clinical investigation for insufficient effectiveness of the device under investigation is defined, the Sponsor reserves the right to discontinue the clinical investigation at any stage or reduce the follow-up period with suitable written notice to the Investigator. A possible reason may include, but is not limited to, the cancellation of further product development.

3.3.1 Subject Follow-up for Suspension or Early Termination of the Study

If the Sponsor suspends or prematurely terminates the clinical investigation at an individual site in the interest of safety, the Sponsor will inform all other Principal Investigators.

If suspension or premature termination occurs, the Principal Investigator or authorized designee will promptly inform the enrolled subjects at his/her site and return patients to their appropriate standard medical treatment with device-related AEs reported to the Sponsor per local vigilance reporting requirements.

A Principal Investigator, IRB/EC, or regulatory authority may also suspend or prematurely terminate participation in the clinical investigation at the investigational site(s) for which they are responsible. The investigators will follow the requirements specified in the Clinical Trial Agreement.

If a suspended investigation is to be resumed, a prior approval should be obtained from the IRB/EC and a notification should be sent to the regulatory bodies as applicable. If subjects were informed of suspension, they shall be informed of the resumption of the clinical investigation.

4.0 ENDPOINTS

The two primary endpoints and the descriptive endpoints in this clinical investigation have been chosen based on safety and performance measures reported in the mechanical heart valve literature.

Clinical Investigation Plan

4.1 Primary Endpoints and Rationale

The primary safety endpoint is freedom from valve-related mortality at 5 years. Reasons for selection of this primary safety endpoint include its correlation with severe device- and procedure-related adverse events and the frequent reporting of this outcome in the published literature on surgical MHVs. [REDACTED]

The primary performance endpoint is freedom from valve-related reoperation at 5 years. Reasons for selection of reoperation on the MHV is an indicator of both the performance and durability of the original MHV implant procedure and is often reported in the published literature on MHVs. [REDACTED]

4.2 Descriptive Endpoints

This section lists descriptive endpoints that will be summarized using descriptive statistics and compared to the objective performance criteria as defined in ISO5840-2:2021 for mechanical heart valves or acceptance criteria if appropriate.

- Annualized rate from the following events from implant through five years post-implant:
 - All-cause mortality
 - Reintervention
 - Major bleeding
 - Thromboembolism
 - Valve thrombosis
 - Endocarditis (Operated Valve)
 - Major Paravalvular Leak
- NYHA (New York Heart Association) Functional Class at baseline and annually post-implant

